Baseline medical and asthma control questionnaires will take 5- 10 minutes to complete, will be completed at the Medical Office Building, in a private office. Questionnaires are in paper format, and will be completed by the participant.

Statistical Considerations: Delineate the precise outcomes to be measured and analyzed. Describe how these results will be measured and statistically analyzed. Delineate methods used to estimate the required number of subjects. Describe power calculations if the study involves comparisons. Perform this analysis on each of the primary and secondary objectives, if possible.

We will compare changes in respiratory system impedance across the 2 levels of PEEP for participants being exposed to methacholine prior to PEEP (visit 4-5) and methacholine simultaneously with PEEP (visits 2-3), separately.

We will also measure symptom scores using the Borg scale; symptom scores in the obese are related to lung reactance, and we anticipate that symptom scores will be decreased by the PEEP intervention and that this will correlate with decreases in measures of impedance.

The primary statistical analysis will be to compare changes in measures of impedance at PEEP 0 versus 10 cmH₂O using paired t-tests. If normal distribution assumptions are not met, variables will be appropriately transformed. We will compare data from visits 2-3, and visits 4-5 as separate experiments, as they address different scientific questions. We will also compare symptom scores (Borg scale) and, FRC at the two different levels of PEEP.

Power Analysis: Based on the preliminary data shown in Figs. 10 & 11 obtained with a PEEP of 10 cmH₂O, we anticipate that a PEEP of 10 cmH₂O will lead to a 50% attenuation in the increase in resistance in response to methacholine compared to the increase in resistance at PEEP 0, which will be our primary outcome of interest. From our prior work using a commercially available forced oscillation system in obese asthmatics,

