we anticipate that the baseline resistance of the respiratory system at a frequency of 5 Hz will be 7.02 ± 1.80 cmH₂O.s/L, and that this will increase to 10.50 ± 2.20 cmH₂O.s/L with a PC₁₀ dose of methacholine at PEEP = 0. Examination of the change in resistance in response to methacholine for PEEP = 0 compared to PEEP = 10 using a paired t-test with a 2.5% Type I error level and $r = 0.50$ within subject correlation indicates that a sample size of $n = 10$ LONA subjects will provide 99% power to detect the postulated within subject change. An independent comparison using a 2.5% Type I error level for the change in resistance prior to methacholine using the smaller effect sizes would require a sample size of $n = 15$ to achieve a 78% power. An adjusted 5% Type I error level was used to compensate for the two separate comparisons conducted for testing the resistance changes. We will increase this to 20 participants to allow for potential drop-outs and any technical difficulties participants experience with completing any of the study visits.

Confidentiality Measures and Secure Storage of Data or Tissue: Describe how the data/tissue will be collected. Will there be identifiers or will the data/tissue be coded? Describe where the data/tissue will be stored and how it will be secured. Describe who will have access to the data/tissue or the codes. If subject data/tissues with identifiers will be released, specify to whom. Describe what will happen to the data/tissues when the research has been completed.

Not Applicable

- Research material obtained from participants will include results of lung function testing, and medical history obtained from direct patient interview.
- People having access to protected data will be the investigators participating in this study and appropriate regulatory authorities.
- Documents containing identifiable information will be kept in a locked file cabinet at the Vermont Lung Center. All participants will be assigned a unique study ID, which be kept in this locked file cabinet. Study specimens will be labeled with the study ID, and not identifiable information. Our study database will be password protected, and participants will be identified in the database only by their unique participants ID.
- Optional Leftover blood samples and data for future research on asthma and obesity will be stored frozen in [name] UVM laboratory bio-repository (CHRMS: 16-636). The samples will be identified with the unique study ID and date only.

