Rationale for Eligibility Criteria: Our prior experience suggests that, if obesity does affect airway compliance, it may take time to develop Accordingly, we exclude participants younger than 18 years old as well as participants with an asthma diagnosis at an age younger than 18 years old. We use IgE as a marker of active allergic disease.

Vulnerable Populations: Explain the rationale for involvement of special classes of subjects, if any. Discuss what procedures or practices will be used in the protocol to minimize their susceptibility to undue influences and unnecessary risk (physical, psychological, etc.).

Not applicable

Number of Subjects: What is the anticipated number of subjects to be enrolled at UVM/UVM Medical Center and in the case of a multi-center study, with UVM/UVM Medical Center as the lead, the total number of subjects for the entire study.

20 total participants are needed to complete the study.

We anticipate that we will need to screen up to 80 subjects to find 20 that are eligible for this study.

Inclusion/Exclusion Criteria: Eligibility and ineligibility criteria should be specific. Describe how eligibility will be determined and by whom. Changes to the eligibility criteria at a later phase of the research have the potential to invalidate the research.

Inclusion Criteria:

- 1. BMI ≥ 30 kg/m²

- 2. ages ≥ 18 years
- 3. ≤ 20 pack year smoking history
- 4. physician diagnosis of asthma at age ≥ 18 years
- 5. IgE <100 IU/ml.

Exclusion Criteria:

- 1. Pregnancy
- 2. other significant lung disease
- 3. unable or unwilling to provide informed consent
- 4. FEV1 < 60% predicted
- 5. Asthma exacerbation (defined as a hospitalization, ED visit, urgent health care visit for asthma or new systemic corticosteroids for asthma) in the prior 6 weeks.

Inclusion of Minorities and Women: Describe efforts to include minorities and women. If either minorities or women are excluded, include a justification for the exclusion.

Women:

We plan to recruit both genders to this study.

Minorities:

We anticipate that we will recruit minorities in proportion to the local population. Vermont is predominantly Caucasian (96.4% Caucasian, 0.9% African American, 1.4% Hispanic), but we have had success in recruiting minorities with outreach to our local community health clinics and targeted advertising to community groups. We will not exclude any racial/ethnic group from this study.

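### The stated 99% power at n = 10 for PEEP 0 versus PEEP 10 does not follow from the stated inputs; if r = 0.50 also links the two changes, a 50% attenuation has about 54% power

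*Combined protocol and SAP*

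**What the plan says.** Under Statistical Considerations, the Power Analysis sets the effect: "we anticipate that a PEEP of 10 cmH₂O will lead to a 50% attenuation in the increase in resistance in response to methacholine", relative to the increase at PEEP 0, and names this the primary outcome of interest. It puts resistance at 5 Hz at 7.02 ± 1.80 cmH₂O.s/L before challenge and says "this will increase to 10.50 ± 2.20 cmH₂O.s/L with a PC₁₀ dose of methacholine at PEEP = 0".

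The test is described as the change in resistance "for PEEP = 0 compared to PEEP = 10 using a paired t-test with a 2.5% Type I error level", with a within-subject correlation of 0.50. On that basis 10 "LONA subjects will provide 99% power to detect the postulated within subject change".

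A second comparison, "for the change in resistance prior to methacholine using the smaller effect sizes", is said to need n = 15 for 78% power. The number is then raised to 20 to cover drop-outs and technical difficulties, and Number of Subjects says that "20 total participants are needed to complete the study". The primary analysis treats the two pairs of visits apart: "We will compare data from visits 2-3, and visits 4-5 as separate experiments, as they address different scientific questions".

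The plan does not give the SD of a change, any resistance value at PEEP 10, the sidedness of the 2.5%, the pair of measurements that r = 0.50 links, or the size of the second effect.

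**The concern.** The test compares two changes, so its power depends on the SD of the difference between them. With a 50% attenuation the difference to detect is only half of the methacholine increase, while each change has an SD of about 2 cmH₂O.s/L when r = 0.50 links its pre and post values. Near-certain power from 10 participants looks too high for that ratio.

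This is the sample-size justification for the primary outcome. A reader who accepts it would conclude that the study could lose half of its 20 participants and still be almost sure to detect the effect. It also leaves unclear which of the two quoted power figures belongs to the PEEP comparison.

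**Working it through.** **Inputs, all from the Power Analysis.** Pre-challenge 7.02, SD 1.80. Post-challenge at PEEP 0 10.50, SD 2.20. Attenuation 50%. Type I error 2.5%. r = 0.50. Two-sided testing is assumed first because sidedness is not stated. Power is exact, from the noncentral t with n − 1 degrees of freedom and noncentrality √n × (difference ÷ SD of the paired difference).

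**Effect and SD of one change**

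- Increase at PEEP 0: 10.50 − 7.02 = 3.48. Half of it: 1.74.
- SD of a pre-to-post change at r = 0.50: √(1.80² + 2.20² − 2 × 0.5 × 1.80 × 2.20) = √4.12 = 2.030.

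**Reproducing the plan's own figures**

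- Full increase: 3.48 ÷ 2.030 = 1.714. At n = 10, power is 99.1%, which matches the stated 99%.
- Half increase: 1.74 ÷ 2.030 = 0.857. At n = 15, power is 78.1%, which matches the stated 78%.

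So one SD and one r reproduce both published figures, but the 99% goes with the whole methacholine increase and the 78% with the 50% attenuation.

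**Power for the stated contrast (difference 1.74)**

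- Reading (i): r = 0.50 among all four measurements, with SDs 1.80 and 2.20 at each PEEP level. Covariance of the two changes: 0.5 × (2.20 − 1.80)² = 0.08. Correlation: 0.08 ÷ 4.12 = 0.019. SD of the difference: √(2 × 4.12 − 2 × 0.08) = 2.843.
- Reading (ii): r = 0.50 pre-to-post and also between two changes of equal SD. SD of the difference: 2.030 × √(2 × (1 − 0.5)) = 2.030.
- Reading (iii): as (ii), but with the PEEP 10 change SD free. The difference SD is smallest when that SD is half the PEEP 0 value: 2.030 × √0.75 = 1.758.

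| Reading | SD of difference | n = 10 | n = 15 | n = 20 | n = 10, one-sided 2.5% |
|---|---|---|---|---|---|
| (i) | 2.843 | 28% | 47% | 62% | 41% |
| (ii) | 2.030 | 54% | 78% | 91% | 68% |
| (iii) best case | 1.758 | 67% | 89% | 97% | 80% |

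Simulation agrees: 0.284, 0.467 and 0.622 for reading (i) at n = 10, 15 and 20, and 0.539 for reading (ii) at n = 10. Under reading (ii), 99% needs 32 pairs.

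**What 99% at n = 10 would require.** The paired-difference SD must be about 1.022.

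- If each change has SD 2.030 and the SDs are equal: correlation between changes 1 − (1.022 ÷ 2.030)² ÷ 2 = 0.873.
- For any PEEP 10 change SD: correlation at least √(1 − (1.022 ÷ 2.030)²) = 0.864.
- If r = 0.50 links only the two changes: pre-to-post correlation 0.888 with equal change SDs, or 0.844 with the PEEP 10 change SD halved.

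**Sensitivity at n = 10, equal change SDs, two-sided**

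| Correlation between changes | 0 | 0.5 | 0.7 | 0.8 | 0.87 |
|---|---|---|---|---|---|
| Power | 28% | 54% | 78% | 92% | 99% |

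**The case against.** The strongest reply is that the 99% is unsupported rather than wrong. The plan does not state the SD of the paired difference, and the effect rests on preliminary figures in a grant application that is not part of these documents. Those data may have supplied a tighter SD or a higher correlation. That is possible, and stating it with its source would settle the point. But the plan presents the 99% as following from r = 0.50, and none of the three readings of that input delivers it, even one-sided.

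One construction does reach 99%. If PEEP exactly halves every participant's increase, with no noise between visits, the difference is 1.74 with SD 2.030 ÷ 2 = 1.015, and power at n = 10 is 99.1%. This implies perfectly correlated changes. Applied to both experiments it would give 99.99% at n = 15 for any degree of attenuation, not 78%. The second comparison might rest on other inputs, so this does not strictly rule it out for the first.

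It is fair to say that 54% depends on using r = 0.50 twice, and that reading (i) reproduces neither published figure and supplies a PEEP 10 SD that the plan does not give. The range of 28% to 67% therefore has to accompany the 54%.

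It is also fair that n = 10 did not set enrolment. The plan goes on to n = 15 and then 20.

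Finally, the 10.50 is tied to a PC₁₀ dose, while Procedures and Study Visits describe the PC₂₀ dose. These sections must be reconciled. All the power figures here inherit that mismatch, and the direction of its effect is unknown.

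**Conclusion.** The concern holds. For a difference of 1.74 at two-sided 2.5%, the stated inputs give 28% to 67% power at n = 10 depending on how r = 0.50 is read, with 54% when it links both pre to post and the two equal-SD changes. One-sided testing raises the range to 41% to 80%. Reaching 99% needs a second correlation of about 0.84 to 0.89 that the plan does not state.

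That the 99% was computed on the full methacholine increase, and that the 78% belongs to the 50% attenuation, is an inference from matching numbers, not something the plan says.

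The consequence for the trial is limited but not settled. With 15 to 20 complete pairs, power for 1.74 is 78% to 91% under reading (ii) but 47% to 62% under reading (i). Whether 20 participants are enough depends on an SD and a correlation that are missing from the plan.

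**What to change.** Keep enrolment at 20 and rewrite the Power Analysis.

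- Remove or correct the claim of 99% with n = 10.
- For each experiment (visits 2-3 and visits 4-5), state the difference to detect, the SD of the paired PEEP 0 minus PEEP 10 difference in changes, the correlation assumed between the two changes (separately from the pre-to-post correlation), and whether the 2.5% is two-sided.
- If r = 0.50 between equal-SD changes was meant, give power as about 54%, 78% and 91% at 10, 15 and 20 complete pairs, labelled as conditional on that assumption. Add the n = 10 sensitivity range: about 28% at a correlation of 0, 78% at 0.7 and 92% at 0.8.
- If a higher correlation was used, state it and its source.
- Put numbers to the smaller effect sizes of the second comparison, say which experiment it covers, and give its power at 15 and 20 pairs.

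The cost is protocol wording and a less favourable stated power. No participants are added and the analysis does not change.

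### The 78% power at n = 15 is the power for the postulated 50% attenuation itself, not for a smaller effect, so it cannot stand as worded beside the 99% at n = 10

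*Combined protocol and SAP*

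**What the plan says.** All of this stands in the Combined protocol and SAP, Statistical Considerations, mostly under Power Analysis.

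- **Effect.** The plan postulates one PEEP effect: "we anticipate that a PEEP of 10 cmH₂O will lead to a 50% attenuation in the increase in resistance in response to methacholine", relative to the rise at PEEP 0. It names this its primary outcome of interest.
- **Means and SDs.** The "baseline resistance of the respiratory system at a frequency of 5 Hz will be 7.02 ± 1.80 cmH₂O.s/L", and "this will increase to 10.50 ± 2.20 cmH₂O.s/L with a PC₁₀ dose of methacholine at PEEP = 0".
- **Test.** The changes at PEEP 0 and PEEP 10 are compared "using a paired t-test with a 2.5% Type I error level and $r = 0.50$ within subject correlation".
- **First power figure.** "n = 10$ LONA subjects will provide 99% power to detect the postulated within subject change".
- **Second power figure.** For a further comparison at 2.5%, described as the change in resistance before methacholine, "using the smaller effect sizes would require a sample size of $n = 15$ to achieve a 78% power". No value is printed for the smaller effects, and no separate SD or correlation.
- **Enrolment.** "We will increase this to 20 participants to allow for potential drop-outs and any technical difficulties".

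The same section analyses visits 2-3 (PEEP with methacholine) and visits 4-5 (PEEP after methacholine) as separate experiments.

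**The concern.** Read in order, the paragraph says that 10 participants give near-certain detection of the 50% attenuation and that 15 give 78% power for something smaller. Both statements use the same test and error level, and only one set of SDs and one correlation are printed. If the 78% in fact belongs to the 50% attenuation, the plan contains no calculation for a smaller effect, and the sentence credits the design with a sensitivity that its inputs do not show.

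The figure carries weight: n = 15 is the larger of the two sample sizes, and enrolment is raised from it to 20. A non-significant result in either experiment will be read against these power statements.

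**Working it through.** **Inputs (Power Analysis).** Baseline 7.02, SD 1.80; after methacholine at PEEP 0 10.50, SD 2.20; r = 0.50; paired t-test at 2.5%; 50% attenuation. The plan does not say whether 2.5% is one- or two-sided. Two-sided reproduces the printed 78%; one-sided gives 87.0% for the same effect and n.

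**Effect.** Rise at PEEP 0 = 10.50 - 7.02 = 3.48. Half of it = 0.50 x 3.48 = 1.74 cmH2O.s/L.

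**SD of the paired difference.** sqrt(1.80² + 2.20² - 2 x 0.50 x 1.80 x 2.20) = sqrt(3.24 + 4.84 - 3.96) = sqrt(4.12) = 2.03.

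**Power.** Noncentral t with n - 1 degrees of freedom, noncentrality (effect/SD) x sqrt(n), two-sided 0.025.

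**Reproducing the plan's figures**

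| n | Effect | Effect/SD | Power | Plan states |
|---|---|---|---|---|
| 15 | 1.74 (50% attenuation) | 0.857 | 78.1% | 78%, for smaller effects |
| 10 | 3.48 (whole rise) | 1.714 | 99.1% | 99%, for the postulated change |
| 10 | 1.74 (50% attenuation) | 0.857 | 53.6% | not stated |

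Solving back from 78% at n = 15 gives effect/SD = 0.8565, or 1.739 cmH2O.s/L, which is 50.0% of 3.48. The rounding band 77.5% to 78.5% corresponds to attenuations of about 49.7% to 50.2%. With one set of inputs, then, both printed figures come out if the first effect is the whole rise and the second is half of it.

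**Smaller effects at SD 2.03**

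| Attenuation | Difference | n = 15 | n = 20 |
|---|---|---|---|
| 50% | 1.74 | 78% | 91% |
| 40% | 1.39 | 57% | 73% |
| One third | 1.16 | 41% | 56% |

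**What the SD of 2.03 assumes.** It is built from the SDs before and after methacholine, so strictly it is the SD of one change at one PEEP level. The planned test compares two changes. With equal SDs and correlation rho between them, the SD of their difference is 2.03 x sqrt(2(1 - rho)), which equals 2.03 only at rho = 0.50. The plan gives no value for rho. At 40% attenuation and n = 15:

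| rho | SD of difference | Power |
|---|---|---|
| 0 | 2.87 | 30% |
| 0.3 | 2.40 | 42% |
| 0.5 | 2.03 | 57% |
| 0.7 | 1.57 | 81% |

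**Alternative reading.** If the second comparison is taken literally as resistance at PEEP 0 versus PEEP 10 before methacholine, with SD 1.80 at both levels and r = 0.50, the SD of the difference is 1.80. Then 78% at n = 15 matches a difference of 1.54.

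**The case against.** The strongest reply is that 78% is not a wrong number. It is the right power for the effect the plan postulates, and the misstated figure is the 99% before it. Once the 99% is seen to rest on the whole 3.48 rise, the smaller effect reads naturally as 1.74. This stands, and it fixes where the error lies: in the effect attached to the 78%, not in the 78%. It does not rescue the text. The postulated change is defined as a 50% attenuation and the 99% is claimed for it, so a smaller effect can only mean one below 50%. Correcting the 99% alone would leave that wording in place.

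A reader might infer that any effect below 50% attenuation must have less than 78% power. The documents do not support that. It holds at SD 2.03, but no SD or correlation is printed for the second comparison; with a correlation of 0.7 between the changes, 40% attenuation has 81% power at n = 15.

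A reader might also take the second figure to describe visits 4-5. The text does not say so: a change before methacholine matches neither analysed experiment, and on the literal reading 78% fits a difference of 1.54. The back-solved 50% is therefore the best match to the printed inputs, not proof of what was computed. The smaller effects may also be defined in the grant application submitted with this form, or in the preliminary figures it cites; neither is reproduced here.

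Finally, 40% and one third are illustrative values. The plan postulates only 50%.

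**Conclusion.** The point holds as a mislabelled power figure. On the printed inputs, 78% at n = 15 is the power for the full 50% attenuation of 1.74 cmH2O.s/L, and 99% at n = 10 is the power for a difference equal to the whole rise. The two statements cannot both be right as worded, and the inputs do not support 78% power for an effect below the postulated one.

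This rests on a two-sided 2.5% test and on r = 0.50 also linking the changes at PEEP 0 and PEEP 10. Under those assumptions 40% attenuation has 57% power with 15 completers and 73% with 20, so the shortfall against 78% is 21 and 5 points; at one third it is 37 and 22 points. The size is sensitive to the correlation, so these are conditional figures.

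It does not follow that the enrolment is inadequate for the plan's own hypothesis. Under the same assumptions power for a 50% attenuation is 78% with 15 completers and 91% if all 20 complete.

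**What to change.** Rewrite the power paragraph as follows.

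1. Delete the reference to smaller effect sizes. State that 15 completers give 78% power, and 20 give 91%, for a 50% attenuation of 1.74 cmH2O.s/L, using a two-sided paired t-test at 2.5% with an SD of the paired difference of 2.03, assuming r = 0.50 also links the changes at PEEP 0 and PEEP 10.
2. Add that under the same assumption power is 57% at 40% attenuation and 41% at one third with 15 completers, and 73% and 56% with 20. Show the dependence on the correlation: at 40% attenuation and n = 15, 30% if it is 0, 42% if 0.3 and 81% if 0.7.
3. Correct the 99% at n = 10 on the same basis: 54% for 1.74.
4. Say which experiment, visits 2-3 or visits 4-5, each power figure covers. If a comparison before methacholine is really meant, print its effect and SD, and give each of the two experiments a power figure of its own.

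If the grant application defines a smaller effect with its own SD, print those values with the power they give. Keep enrolment at 20. The cost is a rewritten paragraph and a less favourable power statement, with no added participants, visits or procedures.

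### The two resistance comparisons are planned at a fixed 2.5% each; this is valid, but Holm's procedure keeps the same 5% overall error and gives the weaker comparison more power at the same sample size

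*Combined protocol and SAP*

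**What the plan says.** Under Statistical Considerations, the analysis text gives the method: "The primary statistical analysis will be to compare changes in measures of impedance at PEEP 0 versus 10 cmH₂O using paired t-tests". It treats prevention (visits 2-3) and reversal (visits 4-5) as distinct: "We will compare data from visits 2-3, and visits 4-5 as separate experiments, as they address different scientific questions". It gives no significance level, no sidedness and no decision rule.

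The error rates appear only in the Power Analysis paragraph. The first comparison is planned "using a paired t-test with a 2.5% Type I error level and $r = 0.50$ within subject correlation" and is said to have 99% power with 10 subjects. The second is described as "An independent comparison using a 2.5% Type I error level for the change in resistance prior to methacholine using the smaller effect sizes" and is said to need 15 subjects for 78% power. The reason for the 2.5% follows: "An adjusted 5% Type I error level was used to compensate for the two separate comparisons conducted for testing the resistance changes". Enrolment is then raised to 20 to allow for drop-outs and technical difficulties. No step-down or other sequential procedure appears anywhere in the document.

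**The concern.** Two tests at 2.5% each hold the overall error at 5%. A fixed split, however, uses 2.5% for the second test even after the first has succeeded. At that point only one hypothesis is left to protect, and it can be tested at the full 5% without breaking the family-wise limit. Holm does exactly this: it rejects whatever the fixed split rejects, and sometimes more. Its error control does not require independence, which matters because the same participants supply both experiments.

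The Objectives list prevention and reversal as two separate aims, so the trial wants an answer to each. One of the two comparisons is planned at 78% power. In a trial this small, the difference between a 2.5% and a 5% threshold for that comparison is not negligible.

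**Working it through.** **Inputs (Power Analysis).**
- Resistance before methacholine: "baseline resistance of the respiratory system at a frequency of 5 Hz will be 7.02 ± 1.80 cmH₂O.s/L".
- Resistance after methacholine: "this will increase to 10.50 ± 2.20 cmH₂O.s/L with a PC₁₀ dose of methacholine at PEEP = 0". The rise is 10.50 − 7.02 = 3.48.
- Postulated PEEP effect: "a PEEP of 10 cmH₂O will lead to a 50% attenuation in the increase in resistance in response to methacholine". Half the rise is 0.5 × 3.48 = 1.74.
- Within-subject correlation 0.50; 2.5% per test; n = 10 and n = 15; enrolment 20.

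**Reproducing the stated powers.** SD of the difference = √(1.80² + 2.20² − 2 × 0.5 × 1.80 × 2.20) = √4.12 = 2.03. Exact power comes from the noncentral t distribution with n − 1 degrees of freedom and noncentrality d√n, two-sided.
- First comparison: d = 3.48 / 2.03 = 1.714, n = 10, power 99.1% (stated 99%).
- Second comparison: d = 1.74 / 2.03 = 0.857, n = 15, power 78.1% (stated 78%).

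Sidedness is not stated. For the second comparison, a one-sided 2.5% test gives 87.0% and a normal approximation 86.0%, so the two-sided t-test is the reading that matches. The 99% matches only with the full rise of 3.48, not with the 1.74 that a 50% attenuation implies.

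**Holm power.** Let b be the power of a test at 2.5% and f its power at 5%. For independent tests, comparison 2 succeeds under Holm with probability b2 + b1 × (f2 − b2).

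*Case A: effects that reproduce the stated powers (3.48 and 1.74).* At n = 15 and n = 20, b1 exceeds 99.9%.

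| n | b2 (fixed 2.5%) | f2 (5%) | Holm, comparison 2 |
|---|---|---|---|
| 15 | 0.781 | 0.870 | 0.781 + 0.9999 × 0.089 = 0.870 |
| 20 | 0.909 | 0.953 | 0.953 |

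The stronger comparison stays above 99.9% under either rule, so power for both equals power for the weaker one. At n = 15, a correlation of 0.5 between the experiments left comparison 2 at 78% (fixed) and 87% (Holm) in simulation.

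*Case B: an assumption that both experiments have the 1.74 effect and are independent.*
- n = 15, per test: 0.781 + 0.781 × (0.870 − 0.781) = 0.850, against 0.781.
- n = 15, both: 0.781² + 2 × 0.781 × (0.870 − 0.781) = 0.749, against 0.781² = 0.610.
- n = 20, per test: 0.949 against 0.909; both: 0.906 against 0.826.
- With correlation 0.5 at n = 15 (simulation), per test 84% against 78%; both 77% against 66%.

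**At least one success.** Under either rule this requires the smaller p-value to pass 2.5%, so it does not change. In case B at n = 15 it is 1 − (1 − 0.781)² = 95.2%.

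**Error rates.** With both nulls true and independent, the fixed split gives 1 − 0.975² = 4.94%. Holm's family-wise error is then the same as that of the fixed split: 4.9%, 4.7% and 3.7% in simulation at correlations 0, 0.5 and 0.9. With one null true and the other effect large, the error on the true null is about 5% under Holm and 2.5% under the fixed split.

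**The case against.** The strongest reply is that nothing in the plan is wrong. A Bonferroni split controls the error it claims to control, and choosing Holm is a refinement. That stands: a reader might infer a flaw in error control, and the document does not support that.

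Second, the 2.5% stands only in the sample-size paragraph. A reader might infer that the analysis is expressly bound to fixed thresholds. In fact the analysis text gives no level at all, and sizing at 2.5% does not rule out a later step-down test. This stands in part: the fixed split is the only rule the document offers, but stating the rule is as much the remedy as changing it.

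Third, a reader might infer that both tests gain and that the planned power for both effects is only 61%. The stated powers do not support this. They give one comparison 99% at n = 10, and that test gains almost nothing. The 61% comes from placing the smaller effect in both experiments. That is a reasonable assumption, because 1.74 is the stated 50% attenuation, but it is not the plan's scenario.

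Fourth, n = 15 is the number left after losses. At the planned enrolment of 20 the weaker test already has 90.9%, and the same formula passes 80% at n = 16 (81.4%). True, although the extra five are explicitly an allowance for losses.

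Fifth, the change is not wholly free. Each additional Holm rejection has a p-value between 2.5% and 5%, so its 97.5% interval includes zero. In case B at n = 15 this is the whole gain in power for both, 75% − 61% = 14% of trials. This stands and must be disclosed.

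**Conclusion.** The point holds as a missed efficiency at low cost, not as an error. On the plan's own stated powers, Holm adds about 9 percentage points to the weaker comparison at n = 15 (78.1% to 87.0%) and about 4 at n = 20 (90.9% to 95.3%). It adds essentially nothing to the stronger one and nothing to the chance of at least one success. The larger gain, 61% to 75% for showing both effects at n = 15, requires the 1.74 effect in both experiments and independence between them.

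The figures rest on two-sided tests and an SD of the difference of 2.03, both chosen because they reproduce the stated powers. Which experiment the second comparison refers to is an inference, because its description as a change before methacholine is unclear. The 5% guarantee covers the two resistance tests only. The analysis text speaks of measures of impedance in general, and a two-test Holm procedure would not extend to any others.

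**What to change.** Add to the analysis section, before any data are analysed: the two primary resistance comparisons, PEEP 0 versus PEEP 10 at visits 2-3 and at visits 4-5, will be tested by the Holm procedure at an overall two-sided 5%; the smaller p-value is tested at 2.5% and, if significant, the larger at 5%.

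Restate power under Holm for each comparison, and say which experiment each power figure belongs to. Add that confidence intervals are for estimation, and that a 97.5% interval may include zero when the second test is rejected at a p-value between 2.5% and 5%.

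The cost is a few sentences and a recalculation, with no added participants, visits or measurements. The price to acknowledge is that intervals and decisions may not match, and that the error for a single true null can rise from 2.5% to 5% while the family-wise 5% is kept.
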